4.6 Response Evaluable Patients

All patients registered on the protocol and completing a minimum of one dose of nivolumab therapy followed by clinical or radiologic assessment of disease status.

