3.0 STUDY POPULATION

3.1 Inclusion Criteria

- 1) Localized urothelial cancer of bladder with presence of transitional cell carcinoma (TCC) component. Mixed histologies are allowed.
- 2) Clinical or pathologic stage T2 –T4 disease including T4a and 4b if feasible to treat with radiation therapy.
- 3) Locoregional lymph node metastases are permitted but patients with distant metastases are ineligible. Imaging to evaluate for distant metastases should consist of a minimum of CT/MRI of abdomen/pelvis or CT urogram and a CXR or CT chest. Patients for which there is clinical suspicion or symptoms of bone metastasis should have a bone scan completed to rule out metastatic disease prior to enrollment on study.
- 4) Agreeable to consider radiation therapy (RT) for the urothelial cancer: patients have to be evaluated by a radiation oncologist and deemed to be candidates for RT.
- 5) The patients must not be candidates for chemotherapy due to at least one of the following reasons:
 - a. Performance status of 2
 - b. Creatinine clearance \leq 60 ml/min as calculated by the Cockcroft-Gault formula.
 - c. Cardiac disease such as NYHA Class III or IV heart failure or cardiac ischemia within the last 12 months, grade 2 or greater neuropathy, or other

comorbidities based on which patient is not considered a candidate for chemotherapy.

- 6) Adequate liver function with alkaline phosphatase, AST and ALT ≤ 3 x upper limit of normal and bilirubin < 1.5 x ULN
- 7) Adequate Bone marrow function defined as absolute neutrophil count $\geq 1500/\text{mm}^3$ and hemoglobin ≥ 9 g/dL and platelets $\geq 100\text{K}/\text{mm}^3$.
- 8) PS of 0-2 by Zubrod score
- 9) Life expectancy of 12 months
- 10) Age ≥ 18 years of age
- 11) Willingness to sign informed consent
- 12) Patients cannot have active autoimmune disease or immunosuppressive conditions.
- 13) Serum creatinine ≤ 1.5 X institutional ULN or creatinine clearance > 40 ml/min as calculated by the Cockcroft-Gault formula.
- 14) In females with childbearing potential, or men with partners of child bearing potential, willingness to use adequate contraception during the treatment period and for a minimum duration of 5 months after last dose of nivolumab.
- 15) Maximal tumor resection has been performed as feasible.

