4.5 Tumor Assessment

Response criteria:

For measurable disease in the bladder and/or lymph node/s, RECIST criteria 1.1 will be used [14].

THE RECIST 1.1 CRITERIA WITH UNIDIMENSIONAL MEASUREMENT ARE TO BE USED FOR MEASURABLE DISEASE RESPONSE EVALUATION

Methods of Assessment

The same method of assessment and the same technique should be used to characterize each identified and reported lesion at baseline and during follow-up. CT is the best currently available and reproducible method to measure lesions selected for response assessment. MRI is also acceptable in certain situations (e.g., for body scans but not for lung). Lesions on a chest X-ray may be considered measurable lesions if they are clearly defined and surrounded by aerated lung. However, CT is preferable.

Baseline Disease Assessment

All baseline evaluations should be performed as closely as possible to the beginning of treatment and never more than 42 days before the beginning of the treatment.

Measurable lesions must be accurately measured in at least one dimension (longest diameter in the plane of measurement is to be recorded) with a minimum size of:

- 10 mm by CT scan (CT scan slice thickness no greater than 5 mm; when CT scans have slice thickness >5 mm, the minimum size should be twice the slice thickness).
- Malignant lymph nodes: To be considered pathologically enlarged and measurable, a lymph node must be ≥ 15 mm in short axis when assessed by CT scan (CT scan slice thickness is recommended to be no greater than 5 mm). At baseline and in follow-up, only the short axis will be measured and followed.

Non-measurable lesions

Non-measurable lesions are all other lesions, including small lesions (longest diameter <10 mm or pathological lymph nodes with 10 to <15 mm short axis), as well as truly non-measurable lesions.

Target Lesions

- All measurable lesions up to a maximum of two lesions per organ and five lesions in total, representative of all involved organs, should be identified as target lesions and recorded and measured at baseline.
- Target lesions should be selected on the basis of their size (lesions with the longest diameter) and be representative of all involved organs, as well as their suitability for reproducible repeated measurements.
- All measurements should be recorded in metric notation using calipers if clinically assessed. A sum of the diameters (longest for non-nodal lesions, short axis for nodal lesions) for all target lesions.

Non-target Lesions

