All lesions (or sites of disease) not identified as target lesions, including pathological lymph nodes and all non-measurable lesions, should be identified as non-target lesions and be recorded at baseline. Measurements of these lesions are not required and they should be followed as 'present', 'absent' or in rare cases, 'unequivocal progression'.

Evaluation of target lesions

Complete Response (CR):

Disappearance of all target lesions. Any pathological lymph nodes (whether target or non-target) must have reduction in short axis to <10 mm.

Partial Response (PR):

At least a 30% decrease in the sum of diameters of target lesions, taking as reference the baseline sum of diameters.

Progressive Disease (PD):

At least a 20% increase in the sum of diameters of target lesions, taking as reference the smallest sum on study (this may include the baseline sum). The sum must also demonstrate an absolute increase of at least 5 mm.

Stable Disease (SD):

Neither sufficient shrinkage to qualify for PR nor sufficient increase to qualify for PD.

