8.4 Analysis

8.4.1 For the Primary Objective, the censored PFS distribution will be summarized with the Kaplan-Meier (K-M) survivorship estimate. A graph of the K-M curve for PFS will be generated along with the Hall-Wellner 95% confidence band, and a display of the number of patients at risk at several time points, below the X-axis. Summary statistics (12-month PFS rate, median PFS, etc.) will be calculated from the K-M life table, each one with its respective 95% confidence interval (CI). To test whether the point estimate of the 12-month PFS rate is statistically significantly greater than the assumed historical reference value of 0.50, the point estimate will be compared to the upper critical value of 0.64 obtained from the “One Arm Survival” program mentioned in Section 8.3.

8.4.2 For Secondary Objective (1) toxicity rates will be estimated among the toxicity evaluable patients (defined in Section 4.7). Frequency distributions of each toxicity type by severity grade will be generated. For a given grade(s), the point estimate of the toxicity rate will be computed, along with its 95% (Wilson type) CI.

8.4.3 For Secondary Objective (2), the ORR will be estimated among the response evaluable patients (defined in Section 4.6), and among all patients. Frequency distributions of best response will be generated for each of those sets of patients. The point estimate of the ORR will be computed, along with its 95% (Wilson type) CI.

8.4.4 For Secondary Objectives (3) and (4), summary statistics of MFS and OS will be calculated from their respective K-M life tables in the similar fashion as described in Section 8.4.1 for OS. K-M graphs of the censored MFS and OS distributions will also be generated.

8.4.5 For Secondary Objective (5), the QOL data will be used to test the following hypotheses:

1. Demographics and clinical variables (age, sex, race/ethnicity) will be related to length of time on trial (i.e., days or weeks);
2. Demographic and clinical variables (cancer stage, performance status, number of comorbidities) will be related to: (a) average levels of QOL; and (b) variability in QOL over the course of the trial.

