We will use a linear mixed-effects model to test the association between baseline patient factors (demographic and clinical measures) and QOL. The model will have a random intercept, slope, and leading coefficient for the measurement of QOL across all 15 time points identified in the Study Calendar, Section 2.3. The patient factors will be used as predictors of QOL with baseline QOL as a covariate. The association will be investigated based on the statistical testing for each of the slope and intercept fixed-effects using a Wald test. As the measurements on each individual would be correlated, the first-order autoregressive AR(1) residual will be used for the residual variance-covariance structure. We will also investigate other variance-covariance residual structures to further improve the model fitting. The final model will be selected based on the Akaike information criterion (AIC).

8.4.6 For Secondary Objective (6), the tissue markers (e.g., PD-1, PDL-1, TILs) and serum marker Th1/Th2 cytokine ratio first will be summarized descriptively. The categorical markers PD-1 and PDL-1 will be summarized via frequency distributions (over their IHC expression categories of 0, 1+, 2+, and 3+). The continuous markers (e.g., TILs, Th1/Th2 cytokine ratio, etc.) will be summarized with standard descriptive statistics. These descriptive analyses of the tissue and plasma biomarkers will be performed for each time point at which the each marker is determined.

Response (CR/PR vs not) will be modeled as a function of a dichotomized version of prestudy PD-1 and PDL-1 expression (separately) using exact logistic regression. Similar logistic model analyses of those tissue markers determined at other time points prior to response determination will also be performed. Similar modeling will be performed for the continuous (ungrouped) markers (e.g., TILs from tissue, and the Th1/Th2 cytokine ratio). The statistical goal of these exploratory analyses is to obtain the point and 95% CI

estimates of the odds ratio (OR), and to simply determine the direction and approximate magnitude of these associations for use in planning a subsequent study.

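### Response is defined only for target lesions, yet both ORR denominators and the marker-response models include patients who may have none

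*Combined protocol and SAP*

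**What the plan says.** - **Response criteria.** Section 4.5 (Tumor Assessment) states: "For measurable disease in the bladder and/or lymph node/s, RECIST criteria 1.1 will be used". Target lesions are drawn from "All measurable lesions up to a maximum of two lesions per organ and five lesions in total". CR is "Disappearance of all target lesions", with an added condition on pathological nodes. PR is "At least a 30% decrease in the sum of diameters of target lesions, taking as reference the baseline sum of diameters". Non-target lesions are only tracked as present, absent or, rarely, clearly progressing. No rule turns that record into a response category.
- **Entry.** No criterion in Section 3.1 asks for measurable disease. Item 15 reads: "Maximal tumor resection has been performed as feasible".
- **Response-evaluable set.** Section 4.6 takes registered patients "completing a minimum of one dose of nivolumab therapy followed by clinical or radiologic assessment of disease status".
- **ORR analysis.** Under Section 8.4.3, "the ORR will be estimated among the response evaluable patients (defined in Section 4.6), and among all patients", with best-response frequencies for both sets and a 95% Wilson interval.
- **Marker models.** Section 8.4.6 states: "Response (CR/PR vs not) will be modeled as a function of a dichotomized version of prestudy PD-1 and PDL-1 expression". It plans similar models for the continuous markers.

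**The concern.** These sections do not fit together. Entry leans towards patients whose bladder tumour has been resected as far as possible. The response scale works only for patients who still have a measurable lesion, and neither ORR denominator removes or otherwise handles the rest.

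ORR is a named secondary endpoint. As written, its value depends partly on how many enrolled patients have residual measurable tumour and on how each site codes those who do not. The same uncertain codes become the binary outcome in the PD-1 and PDL-1 models, whose odds ratios are meant for planning a later study.

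**Working it through.** **Inputs from the plan.** The denominator is N=30 evaluable (Section 8.3). The plan gives no ORR target, null value or power, so there is no ORR figure to reproduce. N=30 itself does reproduce. With exponential PFS, 50% versus 75% at 12 months, 24 months of accrual, 12 of follow-up, one-sided alpha 0.025 and power 0.95, the event probabilities are 0.729 and 0.430 and the log hazard ratio is 0.879. Then n = [(1.960/√0.729 + 1.645/√0.430)/0.879]² = 29.84, rounded up to 30. The ORR question does not depend on this calculation.

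**Assumed inputs.** The share m of patients with measurable disease and the response rate r among them are not in the documents. I take m = 80%, 50% and 30%, and r = 60%, with 80% as a check.

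**Step 1: which categories can a patient with no target lesion receive?**
- PR needs a baseline sum of target diameters. There is none, so PR is impossible.
- CR needs target lesions to disappear. There were none, so the definition neither grants CR nor excludes it.

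**Step 2: ORR under the two possible codings.** Measurable patients = 30m; responders x = 30m × r, rounded.
- Others coded as not CR/PR: ORR = x/30, which cannot exceed m.
- Others coded as CR: ORR = (x + 30 − 30m)/30.

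| m | Measurable | x at r = 60% | Others coded not CR/PR | Others coded CR | Measurable only |
|---|---|---|---|---|---|
| 80% | 24 | 14 | 14/30 = 47% | 20/30 = 67% | 14/24 = 58% |
| 50% | 15 | 9 | 9/30 = 30% | 24/30 = 80% | 9/15 = 60% |
| 30% | 9 | 5 | 5/30 = 17% | 26/30 = 87% | 5/9 = 56% |

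The measurable-only column moves only because x is rounded to whole patients. With r = 80% and the others coded as not CR/PR, the ORR is 19/30 = 63% at m = 80% and 12/30 = 40% at m = 50%.

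**Step 3: precision.** The Wilson interval is [p + z²/2n ± z√(p(1−p)/n + z²/4n²)]/(1 + z²/n), with z = 1.96.
- 9/30: 16.7% to 47.9%, a half-width of about 16 points.
- 9/15: 35.7% to 80.2%, a half-width of about 22 points.

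**Step 4: marker odds ratio, others coded as not CR/PR.** Assume 80% response in marker-positive and 50% in marker-negative measurable patients. The odds ratio is (0.8/0.2)/(0.5/0.5) = 4.0. If a share u of each group is non-measurable, the rates become 0.8(1−u) and 0.5(1−u):
- u = 20%: (0.64/0.36)/(0.40/0.60) = 2.67
- u = 40%: (0.48/0.52)/(0.30/0.70) = 2.15
- u = 60%: (0.32/0.68)/(0.20/0.80) = 1.88

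If the marker has no effect (60% in both groups) but u is 20% in one group and 40% in the other, the odds ratio is (0.48/0.52)/(0.36/0.64) = 1.64.

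**The case against.** **The bias need not be downward.** A reader might infer that patients without a target lesion can never score CR or PR, so that ORR is simply capped and these patients are false non-responders. The text does not go that far. Only PR is ruled out. The CR definition reaches beyond target lesions in its condition on nodes, non-target disease can be recorded as absent, and Section 4.6 accepts clinical assessment. A site could call such a patient a CR. This objection stands: the direction of bias is open. It does not remove the gap, because the result then depends on site judgement.

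**The number affected may be small.** Resection is required only as feasible, and entry allows T2 to T4b disease and regional nodes, so many patients may keep measurable tumour. This also stands. The shares and the 60% rate above are assumptions. The one bladder chemoradiation response figure in the documents, 11 of 13 evaluable patients (Section 1.2), comes from a different regimen and does not settle either value.

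**The consequences are limited.** ORR has no decision rule, the marker models are labelled exploratory, and an all-patient ORR is a common conservative summary. When measurability is unrelated to the marker, the odds ratio is weakened but keeps its direction; the spurious 1.64 needs an assumed imbalance. All true, but the models are meant to give direction and approximate size, and the size is affected even without imbalance.

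**Bladder outcome is captured elsewhere.** Residual invasive disease at post-therapy cystoscopy and biopsy counts as progression (Section 4.9). That serves PFS. Nothing carries it into the response categories.

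**Conclusion.** The concern holds as a mismatch between Sections 4.5, 4.6, 8.4.3 and 8.4.6. For patients without a target lesion, PR is impossible and CR undefined, yet they sit in both ORR denominators and in the CR/PR-versus-not models. The documents do not support the stronger reading that ORR is necessarily biased downward.

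The size cannot be determined from the documents. Under the assumed inputs, the same 60% response in measurable disease could be reported as anything from 17% to 87%, depending on the measurable share and the coding. The marker figures also rest on assumed response rates. The primary PFS analysis is untouched. This merits correction before analysis but does not threaten the trial's main conclusion.

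**What to change.** Amend Sections 4.6, 8.4.3 and 8.4.6:

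1. Define the main ORR set, and the set for all response-marker models, as patients who started nivolumab and had at least one target lesion at baseline.
2. Count patients in that set who are not re-assessed as non-responders. This replaces the post-dose assessment condition in Section 4.6, so that early loss does not raise the rate.
3. Report how many patients had no measurable disease. If an all-patient ORR is kept as a supplement, state how these patients are coded.
4. For patients without measurable disease, report tumour-free versus residual tumour from the cystoscopies and biopsies already scheduled in Sections 2.3 and 4.4. Keep this descriptive and separate from ORR, and note that tumour-free status partly reflects the earlier resection.

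No new procedures are needed. The cost is a smaller denominator for ORR and for the marker models, and a wider ORR interval: about ±22 points at n=15 against ±16 at n=30 in the 50% illustration.

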4.7 Toxicity- Evaluable patients

All patients registered on the protocol and starting therapy with nivolumab will be considered toxicity evaluable.

4.8 Metastasis-Free Survival (MFS)

The time from start of therapy to the appearance of metastases or cancer related death.

4.9 Progression-Free Survival (PFS)

PFS will be measured from treatment start date to date of first documented disease relapse/progression, or death from urothelial cancer whichever occurs first. If patients have residual invasive disease noted at cystoscopy and biopsy post therapy they are deemed to have disease progression at the time of the procedure. After treatment is discontinued/completed, patients will be followed every 3 months for progression and survival for a maximum of 5 years.

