1.2 Background

The standard management of localized urothelial cancer of bladder consists of neoadjuvant chemotherapy followed by radical cystectomy [1]. If patients wish to pursue a bladder sparing procedure then regimens of either 5FU and mitomycin, or cisplatin concurrently with radiation therapy (RT) are accepted therapeutic approaches [2]. However, these regimens are not feasible in a subset of bladder cancer patients who are ineligible for chemotherapy. Bladder cancer is a disease of the elderly and the incidence increases with increasing age. The median age of incidence of bladder cancer is 73 years and 9 of 10 cases occur in patients over the age of 55 years. In addition, the bladder cancer population has a very high rate of associated comorbidities such as renal dysfunction, cardiac and vascular disease and neuropathy which are frequently deterrents to administering chemotherapy. In

some series the patients who are not candidates for cisplatin based therapy due to comorbidities range up to about 40-50% of the patients presenting with localized disease. The morbidity of bladder cancer is frequently significant, with hematuria, urinary obstruction and renal dysfunction being the common and recurring complaints. Cisplatin based therapy concurrently with RT, has demonstrated results comparable to the surgical series; however, the toxicity rates are significant and about 40% of the patients are not candidates for chemotherapy [3,4]. A concurrent regimen of 5FU and mitomycin with RT [5] showed improved outcomes when compared to RT alone; however, the severe toxicity rates of 36% are a definite deterrent. We have reported on a case series of 13 patients receiving concurrent capecitabine and RT in localized bladder cancer, in whom we observed reasonable palliation and response rates [6]. 11 of 13 evaluable patients demonstrated a response and at a median follow up of 10 months only 3 had relapsed. The most common overall toxicities were fatigue (43%), diarrhea (Grade 2, 14% and Grade 3, 29%), and dehydration (43%), with no Grade 4 or 5 toxicities. The therapy options for treatment of symptomatic bladder cancer in patients who are ineligible for chemotherapy demonstrate suboptimal efficacy and hence there is an unmet need to improve the therapeutic outcomes within this patient population.

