4.10 Overall Survival (OS)

OS will be measured from treatment start date to death or last follow up. After treatment is discontinued for any reason, patients will be followed every 3 months for progression and survival for a maximum of 5 years.

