8.3 Design

This is a 1-arm 1-stage survival type design focused on the primary endpoint of the 12-month PFS rate. The study design assumptions are:

- 1) A population reference value of 50% 12-month PFS rate from standard of care with RT alone (from Supplementary Appendix Figure 1(a) in reference [4]);
- 2) A hypothesized 75% 12-month PFS rate for patients treated with Nivolumab+RT;
- 3) Exponentially distributed PFS times;
- 4) Accrual time of 24 months;
- 5) An additional follow-up time of 12 months for all patients;
- 6) Significance level alpha = 0.025 (1-sided, due to the directional hypothesis);
- 7) Power = 0.95 (high due to the unmet need for improved therapy options for study eligible patients).

Under these 7 assumptions, the study will require N=30 evaluable patients, as calculated using the “One Arm Survival” program on the www.crab.org website. Evaluable for

PFS and toxicity evaluable (see Section 4.7) have the same definition: registered and having started Nivolumab therapy. Allowing for up to 10% of enrolled patients who may become inevaluable, up to 34 patients may need to be enrolled.

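### PFS (4.9) and MFS (4.8) count only cancer deaths and no rule covers other deaths; if these are censored, the 12-month PFS rate is overstated and, near 0.64, one or two can reverse the result

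*Combined protocol and SAP*

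**What the plan says.** Section 8.2.1 sends the reader to Section 4.9 for the primary endpoint. There, PFS runs from treatment start to first documented relapse or progression, "or death from urothelial cancer whichever occurs first". Residual invasive disease at a post-therapy biopsy also counts as progression. MFS in Section 4.8 is "The time from start of therapy to the appearance of metastases or cancer related death". Only overall survival carries no restriction on cause: "OS will be measured from treatment start date to death or last follow up" (Section 4.10).

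For the analysis, Section 8.4.1 states that "the censored PFS distribution will be summarized with the Kaplan-Meier (K-M) survivorship estimate" and that, for the test, "the point estimate will be compared to the upper critical value of 0.64". Section 8.3 sets the null as "A population reference value of 50% 12-month PFS rate from standard of care with RT alone" and the alternative as "A hypothesized 75% 12-month PFS rate for patients treated with Nivolumab+RT". It does not say which deaths either rate counts.

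The plan contains no rule for a non-cancer death in PFS or MFS, no procedure for assigning a death to urothelial cancer or to something else, and no sensitivity analysis that counts all deaths. The physician judgement in Section 5.5 concerns relation to study drug, which is a different question.

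**The concern.** A patient who dies of another cause without progression is not a PFS event under 4.9. If that patient is censored, Kaplan-Meier treats the patient as someone who could still have been progression-free at month 12. The estimate is then a net rate, in which non-cancer death is assumed away, and not the proportion alive and progression-free that a reader expects under the label PFS.

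Such deaths are foreseeable here. Section 1.2 says that "the bladder cancer population has a very high rate of associated comorbidities such as renal dysfunction, cardiac and vascular disease and neuropathy". Section 3.1 accepts serious cardiac disease as a reason for chemotherapy ineligibility, and Appendix C reports fatal immune-mediated reactions to nivolumab. On the literal text, a fatal toxicity before progression would not register as a failure of the primary endpoint. In a single-arm trial of 30 patients with a fixed bar, the assigned cause of one or two deaths could decide the conclusion.

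**Working it through.** **Inputs.** From Section 8.3: N = 30, null 0.50, alternative 0.75, exponential times, accrual 24 months, follow-up 12 months, one-sided alpha 0.025, power 0.95. From Section 8.4.1: bar 0.64. Non-cancer mortality is not in the documents; 2%, 5% and 10% at 12 months are assumptions.

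**1. The plan's own figures.** With uniform accrual, the expected event fractions are 0.729 (null) and 0.430 (alternative), and ln(HR) = 0.879.

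n = [1.960/√0.729 + 1.645/√0.430]² / 0.879² = 29.84, so 30, with power 0.951.

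The critical 12-month rate at N = 30 is 0.634 on the log-hazard scale and 0.643 on the cube-root scale. The stated 30 and 0.64 therefore reproduce.

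**2. Effect in a single trial.** Take 30 patients all followed to month 12, with e cancer events and d non-cancer deaths. Counting all deaths, the rate is (30 − e − d)/30. With the d deaths censored, the Kaplan-Meier rate depends on the order of events. It is lowest if the deaths come first, (30 − e − d)/(30 − d), and highest if they come last, (30 − e)/30.

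| Alive and progression-free | d | e | All deaths counted | Non-cancer deaths censored |
|---|---|---|---|---|
| 19 | 1 | 10 | 0.633, fails | 19/29 to 20/30 = 0.655 to 0.667, passes |
| 18 | 2 | 10 | 0.600, fails | 18/28 to 20/30 = 0.643 to 0.667, passes |
| 18 | 1 | 11 | 0.600, fails | 18/29 to 19/30 = 0.621 to 0.633, fails |
| 17 | 2 | 11 | 0.567, fails | 17/28 to 19/30 = 0.607 to 0.633, fails |
| 17 | 3 | 10 | 0.567, fails | 17/27 to 20/30 = 0.630 to 0.667, depends on order |

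The low end for 18/30 is 0.6429, which clears 0.64 by only 0.003.

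**3. Chance of reaching 0.64 when the treatment adds nothing.** Constant hazards, independent non-cancer mortality m at 12 months, non-cancer deaths censored, 200,000 simulated trials per case.

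- *If the 50% counts all deaths*, the true alive-and-progression-free rate is 0.50 and Kaplan-Meier tends to 0.50/(1 − m).
- *If the 50% is cause-specific*, Kaplan-Meier tends to 0.50 and the true alive-and-progression-free rate is 0.50 × (1 − m).

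| m | K-M limit, all-deaths reference | Chance of passing | Alive and progression-free, cause-specific reference | Chance of passing |
|---|---|---|---|---|
| 0 | 0.500 | 0.049 | 0.500 | 0.049 |
| 2% | 0.510 | 0.07 | 0.490 | 0.055 |
| 5% | 0.526 | 0.10 | 0.475 | 0.06 |
| 10% | 0.556 | 0.18 | 0.450 | 0.07 |

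The starting value agrees with the exact binomial P(X ≥ 20 of 30 at 0.50) = 0.049. Its distance from the stated 0.025 exists with no non-cancer deaths at all and is a separate matter.

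**4. Cost of counting every death.** If the 75% was meant as a cancer-only rate, the any-cause rate is 0.75 × (1 − m) = 0.735, 0.7125 or 0.675. The exact chance of at least 20/30 falls from 0.894 to 0.854, 0.779 or 0.623.

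**The case against.** Four objections carry weight.

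- **Censoring is inferred.** Section 8.4.1 speaks of a censored distribution but never says that non-cancer deaths are censored. This stands, and it is why the claim is conditional. The plan would still need to say what it intends.
- **The exposure may be small.** Section 3.1 requires a 12-month life expectancy and Section 3.2 excludes uncontrolled intercurrent illness. Residual invasive disease at the week 13, month 6 and month 12 biopsies is progression, so many failures will be recorded before any later death. All of this stands and limits how many such deaths can matter. Toxic deaths also remain in OS and in the toxicity analysis.
- **The zone of reversal is narrow.** Only 18/30 and 19/30 reverse with one or two deaths. At a true rate of 0.75, those two counts together have probability about 0.08, before requiring that any failure be a non-cancer death. The bar is printed to two decimals; at 0.643 the least favourable ordering from 18/30 would fail. This stands too.
- **The reference may use the same definition.** If the 50% also counts only cancer deaths, the test compares like with like and little inflation remains (0.055 to 0.07 against 0.049).

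The last objection answers a stronger reading that a reader might infer: that the definition demonstrably inflates the false-positive rate. The documents do not support that. Section 8.3 takes the 50% from a figure in a cited source without giving its event definition, and no non-cancer mortality is stated. The objection does not rescue the label: a result reported as PFS would still exceed the proportion alive and progression-free.

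**Conclusion.** The point holds as a defect in the primary endpoint definition and should be fixed. Read literally, 4.9 does not count a comorbid or toxic death before progression as a failure, and no passage says what happens to it. If it is censored, the reported 12-month rate is too high as a measure of patients alive and progression-free. Near the bar, one such death (at 19/30) or two (at 18/30) turns a failed trial into a positive one. These results assume 30 patients with complete follow-up to month 12.

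An effect on the false-positive rate is hypothetical: about 0.07, 0.10 or 0.18 at assumed mortality of 2%, 5% or 10% if the reference counts all deaths, and 0.055 to 0.07 if it does not. Nor should a reader attribute the gap between 0.025 and 0.049 to this definition. For MFS the matter is one of consistency only, since MFS has no decision threshold.

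**What to change.** The order of the steps matters.

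1. **Section 8.3, first.** State which deaths the 50% reference counts, and that the 50% and 75% use the same definition.
2. **Sections 4.9 and 4.8.** Count death from any cause as an event, and report the any-cause 12-month rate as the result labelled PFS.
3. **Section 8.4.1, comparison.** If the 50% counts all deaths, or this cannot be established, compare any-cause PFS with 0.64. If the 50% is cause-specific, also report the cause-specific Kaplan-Meier rate and make the comparison with 50% on that definition, with a short written rule for assigning cause of death.
4. **Any cumulative-incidence analysis.** Label it as describing cancer failure only. One minus the cumulative incidence also treats non-cancer deaths as non-failures: with 10 cancer events and 2 other deaths it gives 1 − 10/30 = 0.667, although 18/30 = 0.600 are alive and progression-free. It cannot stand in for any-cause PFS.
5. **Section 8.4.1, censoring.** State that patients alive without progression are censored at their last disease assessment.

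No new data are needed, since deaths are already followed for OS. The cost is that the observed rate falls if such deaths occur. If the 75% was meant as cancer-only, the chance of at least 20/30 drops from 0.89 to 0.85, 0.78 or 0.62 at 2%, 5% or 10% non-cancer mortality. The power, and with it N = 30 and the 75% alternative, must then be restated.
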